5 SEQUENCE OF PLANNED ANALYSES

5.1 INTERIM ANALYSES

There are no planned Interim Analyses for this study.

5.2 FINAL ANALYSES AND REPORTING

All final, planned, analyses identified in the protocol and in this SAP will be performed after the last subject has completed their final visit and the database is locked. Key statistics and study results will be made available following database lock and statistical analysis on the locked database. Any post-hoc, exploratory analyses completed to support planned study analyses, which were not identified in this SAP, will be documented, and reported as necessary. Any results from these unplanned analyses will also be clearly identified as post-hoc analyses.

6 ANALYSIS POPULATIONS

6.1 INTENT TO TREAT POPULATION (ITT)

The intent-to-treat (ITT) population for this study includes all enrolled subjects. Subjects are considered enrolled in the trial after they have signed the informed consent form and are not screening failures.

6.2 EVALUABLE POPULATION

The evaluable population for this study includes all ITT subjects who undergo cognitive testing with both DCTclock-pen and DCT-clock table and the Linus Platform tests. Given that no initial tablet model needs to be trained, the evaluable population is the primary analysis population for effectiveness.

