### 5.3 STRATEGIES FOR RECRUITMENT AND RETENTION

The target evaluable sample size for analysis is 175. 200 participants will be screened. The anticipated accrual rate is 22 participants per month. Enrollment will be completed in ~9 months.

One to three US sites will be used in this study with competitive enrollment. Participants will be recruited from the general population and referred from neurology clinics in order to recruit subjects with a range of cognitive function. The study will be advertised in these areas using local fliers and print ads in regional papers. Participants will also be approached for participation if they are participating in other research at the sites that does not include the use of a drug or intervention to alter cognitive function and if the participant has not received a Clock Drawing Test within 6 months.

Participants will be compensated for their time at a rate of \$150 for two completed study visits. Subjects will receive \$60 for the first completed study visit and \$90 for the second completed study visit. Transportation costs will also be covered up to \$75 per study visit at the site's discretion. Maximum total payment is \$300 per subject for two completed visits. Payments will be made to the subject at the end of each visit. The study stipend may be prorated if the subject chooses not to complete all tasks on a given study visit.

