**10.2 ANALYSIS DATASETS**

- Intention-to-Treat (ITT) Analysis Dataset: all enrolled participants.
- Evaluable analysis dataset: all enrolled participants undergoing cognitive testing with both DCTclock-pen and DCTclock-tablet and the Linus Platform tests.
- Validation dataset: A randomly selected subset of 50 subjects from the Evaluable Analysis Dataset. This is the primary analysis set for effectiveness.
- Training dataset: Subjects from the Evaluable Analysis Dataset that were not selected for the validation dataset.
- DCTclock and Linus Platform safety analysis dataset: all enrolled participants undergoing cognitive testing with DCTclock (DCTclock-pen and/or DCTclock-tablet) and the Linus Platform tests. This is the primary analysis set for safety.

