6.5 SAFETY POPULATION

The safety population includes all ITT subjects who undergo cognitive testing with DCTclock (DCTclock-pen and/or DCTclock-tablet) and/or the Linus Platform tests. The safety population is the primary analysis population for safety.

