7.2 DISPOSITION OF SUBJECTS AND WITHDRAWALS

All subjects who were screened will be accounted for. The number of subjects who were screened, eligible, in the ITT Population, in the Evaluable Population, in the Validation Population, in the Training Population, and in the Safety Population will be presented by randomized group (tablet-pen vs. pen-tablet) and overall (both randomized groups combined). The number and percent of ITT subjects who attended visit 1 and who attended visit 2 will be presented by randomized group and overall. This by-visit breakdown will be repeated for the Evaluable and Safety Populations.

The number and percent of ITT subjects prematurely withdrawing will be presented overall, by timing of withdrawal (during first visit, after first visit and before second visit, during second visit) and by reason for withdrawal (Subject did not want to complete this testing session; Subject did not want to return for a second testing session; Subject did not show up for scheduled testing session and could not be reached for rescheduling within the time window; PI felt that it was not in the best interest of the subject to continue in the study; Subject met exclusion criteria during visit 2; None given; Other) for each randomization group and overall.

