9 EFFECTIVENESS ANALYSES

9.1 PRIMARY EFFECTIVENESS VARIABLE AND ANALYSES (CONSTANT VARIANCE)

Agreement of DCTclock-pen and DCTclock-tablet in assessing cognitive impairment will be assessed by using the Bland-Altman method on the DCTclock total score. The following hypothesis test will be carried out:

$$H_0: Lower_{LoA} \leq -\delta \text{ or } Upper_{LoA} \geq \delta$$

$$H_1: -\delta < Lower_{LoA} < Upper_{LoA} < \delta$$

where $\delta = 30$ is the pre-specified maximum allowable difference, $Lower_{LoA}$ is the lower bound of the two-sided 95% LoA, $Upper_{LoA}$ is the upper bound of the two-sided 95% LoA. The conclusion that the two measurements are in agreement (i.e. equivalent) depends on whether the two-sided 95% CIs of each (lower, upper) LoA are within the boundaries set from the maximum allowable difference.

Specifically, Bland-Altman analysis will consist of the following:

1. Calculate the paired difference in scores between the two tests (i.e., Discrepancy scores) for each subject.
2. Calculate the mean of these paired differences.
3. Calculate the average of the two test results for each subject.
4. Plot the paired differences (y-axis) vs. the average of the two test results (x-axis). This is commonly called the Bland-Altman plot.
5. Calculate a two-sided 95% LoA of the paired differences as: mean difference +/- 1.96*standard deviation (sd) of the differences.

6. Calculate two-sided 95% CI of each (lower, upper) LoA. The formulas for calculating these CIs are as follows:

*Lower: mean difference – 1.96 * sd – (t0.975, N – 1) * sd * sqrt(1/N + 1.96²/(2 * (N – 1))).*

*Upper: mean difference + 1.96 * sd + (t0.975, N – 1) * sd * sqrt(1/N + 1.96²/(2 * (N – 1))).*

where $t0.975, N – 1 * sd$ is the upper 0.025 critical value of the t distribution with $N-1$ degrees of freedom and where N is the sample size.

7. The conclusion that the two measurements are in agreement (i.e. equivalent) depends on whether the CIs constructed from the data are within the boundaries set from the maximum allowable difference. Success is declared on the primary endpoint if the lower CI of the lower LoA is >-30 , and the upper CI of the upper LoA is $<+30$.

The Evaluable Population will be used for these analyses.

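### The primary effectiveness population carries an undefined Linus Platform condition that the pen-tablet comparison does not need

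*SAP*

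**What the plan says.** SAP 6.2 admits to the Evaluable Population ITT subjects "who undergo cognitive testing with both DCTclock-pen and DCT-clock table and the Linus Platform tests", and adds that "the evaluable population is the primary analysis population for effectiveness". Protocol 10.2 defines the set in the same three parts: "all enrolled participants undergoing cognitive testing with both DCTclock-pen and DCTclock-tablet and the Linus Platform tests".

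The primary analysis in SAP 9.1 begins "Calculate the paired difference in scores between the two tests (i.e., Discrepancy scores) for each subject" and needs nothing beyond the pen and tablet total scores. On the set to be used, it says "The Evaluable Population will be used for these analyses". Sections 9.2, 9.3 and 11.3 name the same population. SAP 7.3 rules out imputation. No analysis of all available pairs is planned.

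The SAP's safety population (6.5) is worded more loosely, covering subjects tested with DCTclock ("DCTclock-pen and/or DCTclock-tablet) and/or the Linus Platform tests". Neither document says which Linus tests, how many, or at which visit, a subject must have taken to be evaluable.

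**The concern.** A pair of DCTclock scores is all that a Bland-Altman analysis can use. A further entry condition can only remove usable pairs, and membership of the primary set then depends on how an undefined phrase is read, possibly after the data have been seen.

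The condition looks inherited. In protocol 10.2 and 10.3.1 the evaluable set was the pool from which Linus algorithms were to be trained and validated, where requiring Linus data makes sense. The SAP's document history records that the Evaluable Population became the primary set because no tablet model would be trained. The Linus condition stayed.

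If subjects without full Linus data also had more variable pen-tablet differences, leaving them out would make the limits of agreement too narrow. Aim 1 is equivalence across diverse levels of impairment, so such a selection would matter.

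**Working it through.** **1. Can a complete pair exist with incomplete Linus data?** Visit 2 in protocol 7.3.2 has 92 minutes of assessments, with DCTclock first (5 minutes). The Linus items after it take 15 + 10 + 10 + 10 + 5 + 5 + 2 = 57 minutes. RBANS, which is not part of the evaluable definition, takes the other 30, and 5 + 57 + 30 = 92. The documents provide for incomplete sessions in three places:
- Protocol 2.3.1 has subjects stop a standing or walking task that makes them uncomfortable.
- Protocol 5.3 says "The study stipend may be prorated if the subject chooses not to complete all tasks on a given study visit".
- SAP 7.2 lists "Subject did not want to complete this testing session" among the withdrawal reasons.

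So the case can arise.

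**2. Does the clause exclude such a subject?** That depends on the reading.
- *All tests required:* yes. Eye tracking and all speech tasks except list learning are given only at Visit 2, so missing one of them is enough.
- *Any test suffices:* almost never. Linus drawing, reaction-time and gait tests are scheduled at Visit 1, and the Linus wave-copying pre-test (protocol 6.1) comes before DCTclock-tablet.

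**3. The plan's own figure.** SAP section 4 gives 41 evaluable subjects for at least 90% power, with mean difference 10, SD 7 and margin 30. By the noncentral-t formula:
- SE = 7 × sqrt(1/41 + 1.96²/80) = 1.884
- noncentrality = (30 − 10 − 1.96 × 7)/1.884 = 3.334
- critical t on 40 df = 2.021
- power = 0.902, and 41 is the smallest n that reaches 0.90

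The figure reproduces. Simulating the 9.1 decision rule gives 0.875 at 41, but 0.9998 with 125 pairs, so losing some of the 175 costs almost no power.

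**4. Possible effect on the limits.** The documents give no figures for this. Assume 175 pairs, a share p lost, SD 12 in the lost pairs and 7 in the rest, and the same mean difference of 10 in both.
- Full-set SD = sqrt((1 − p) × 49 + p × 144)
- Upper confidence bound of the upper limit = 10 + s × (1.96 + t × sqrt(1/n + 1.96²/(2(n − 1)))). At n = 175 this is 10 + 2.2155s.
- After exclusion, SD is 7 and the half-width is 1.96 × 7 = 13.72.

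| p | Full-set SD | Half-width | Understated by | Upper bound, full set |
|---|---|---|---|---|
| 2% | 7.13 | 13.98 | 0.3 | 25.8 |
| 5% | 7.33 | 14.37 | 0.6 | 26.2 |
| 10% | 7.65 | 14.99 | 1.3 | 26.9 |

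After exclusion the upper bound is 25.5 to 25.6. All of these are below 30. The standard errors grow by sqrt(1/(1 − p)), that is 1% to 5%.

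**5. What would it take to change the result?** At mean 10 and n = 175 the criterion is met up to SD = 20/2.2155 = 9.03. For the full set to fail, the lost pairs would need SD = sqrt((9.03² − (1 − p) × 49)/p), which is about 41, 26 and 19 for p = 2%, 5% and 10%.

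A wider grid of 24 cases assumed 20% or 30% of subjects impaired, SD 10 to 14 in them and 7 in the others, and 10% to 50% of the impaired pairs lost. The upper bound fell by 0.1 to 2.0 points. One case moved from fail to pass (31.38 to 29.37): 30% impaired, SD 14, half of them lost.

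**The case against.** The strongest reply is that the clause asks only that subjects undergo Linus testing, not that they finish every task at both visits. A subject who stops after DCTclock at Visit 2 would normally have taken Linus tests at Visit 1, and so would be evaluable. The withdrawals shell in the SAP appendix is to be repeated for the Evaluable Population and has a row for leaving during the second visit, which also leans towards the lenient reading. That stands as a reading, but the text does not settle it. The looser conjunction in 6.5 shows that the authors could have written 6.2 that way.

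A reader might infer more: that valid pairs will be lost, mainly among impaired subjects, and that this favours success. The documents do not support that. They give no count of lost pairs and no statement about who would be lost, and the provisions for incomplete sessions are contingencies rather than forecasts. Nor is the direction fixed. SAP 9.2 lets the SD vary with the average score through linear and squared terms, displayed over 0 to 100. If scores are bounded there, averages near 0 force small differences, and losing very impaired subjects could widen the limits.

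Selection would also be partly visible already. ITT and Evaluable counts are tabulated, as are demographics and MMSE for both populations. However, no table counts complete pairs that fall outside the Evaluable Population.

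**Conclusion.** The point holds as a fault in the definition of the primary set: it imposes a condition that the analysis does not need and does not say what the condition requires. It does not hold as a demonstrated bias. On the strict reading complete pairs can be excluded; on the lenient reading almost none are.

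If the lost pairs were more variable, the limits would be somewhat too narrow: by 0.3 to 1.3 points of half-width under the assumed 2% to 10% loss and SD 12 against 7, with the equivalence conclusion unchanged at a mean difference of 10. Under equal variances and means there is no such bias. Power is unaffected in practice. The change is worth making because it costs no subjects, visits or power and removes the ambiguity before it can matter.

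**What to change.** - For SAP 9.1 to 9.3 and the pen-tablet model in 11.3, define the analysis set as all ITT subjects with both a DCTclock-pen and a DCTclock-tablet total score. Section 11.3 extends the 9.2 model, so the two should share a set.
- In 6.3, draw the contingent validation set for the DCTclock comparison from that same set.
- Keep the Linus condition only for 11.1 and 11.2.
- Record the departure from protocol 10.2 in SAP section 12.

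The cost is a few sentences of text. N may differ between the primary and exploratory tables, which a footnote can explain.

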6.3 VALIDATION POPULATION

The validation population is a randomly selected subset of 50 subjects from the evaluable population. If there is a need to train a tablet specific model, this will become the primary population for evaluating effectiveness.

6.4 TRAINING POPULATION

The training population consists of subjects from the evaluable population that were not selected for the validation population.

6.5 SAFETY POPULATION

The safety population includes all ITT subjects who undergo cognitive testing with DCTclock (DCTclock-pen and/or DCTclock-tablet) and/or the Linus Platform tests. The safety population is the primary analysis population for safety.

7 GENERAL ISSUES FOR STATISTICAL ANALYSIS

Descriptive statistics (mean, standard deviation, frequencies, etc.) for baseline subject characteristics, subject disposition and other relevant study parameters will be reported.

7.1 ANALYSIS SOFTWARE

Analysis data sets, statistical analyses and associated output generated by Linus Health will be generated using R version 4.1.

7.2 DISPOSITION OF SUBJECTS AND WITHDRAWALS

All subjects who were screened will be accounted for. The number of subjects who were screened, eligible, in the ITT Population, in the Evaluable Population, in the Validation Population, in the Training Population, and in the Safety Population will be presented by randomized group (tablet-pen vs. pen-tablet) and overall (both randomized groups combined). The number and percent of ITT subjects who attended visit 1 and who attended visit 2 will be presented by randomized group and overall. This by-visit breakdown will be repeated for the Evaluable and Safety Populations.

The number and percent of ITT subjects prematurely withdrawing will be presented overall, by timing of withdrawal (during first visit, after first visit and before second visit, during second visit) and by reason for withdrawal (Subject did not want to complete this testing session; Subject did not want to return for a second testing session; Subject did not show up for scheduled testing session and could not be reached for rescheduling within the time window; PI felt that it was not in the best interest of the subject to continue in the study; Subject met exclusion criteria during visit 2; None given; Other) for each randomization group and overall.

7.3 METHODS FOR WITHDRAWALS AND MISSING DATA

Subjects who withdraw or terminate from the study will not be pursued as the study has no follow-up or long-term safety and effectiveness endpoints. Subjects who withdraw or do not complete the second visit will not be replaced as the overall sample size will take into account potential withdrawals. There will be no imputation of missing data in the analyses.

7.4 PROTOCOL DEVIATION

A listing of protocol deviations for the ITT Population will be created which will include randomization group, site, subject ID, whether or not the subject is in the Validation Population, protocol deviation #, type of deviation, date of deviation, time of occurrence, reason for deviation and the justification/corrective action.

7.5 MULTIPLE COMPARISONS AND MULTIPLICITY

There is one primary effectiveness analysis. There are several secondary and exploratory effectiveness analyses; there will be no adjustment for multiple comparisons across these analyses.

7.6 TIMING OF ASSESSMENTS AND EVENTS FOR ANALYSIS

Per the protocol, Study Day 0 is the date the index procedure (a.k.a. Visit 1 which consists of screening and the first set of study assessments). Study days will be calculated as follows:

Pre-index procedure, Study Day = Assessment Date – Index Procedure Date

Post-index procedure, Study Day = Assessment Date – Index Procedure Date

Visit 2 will take place between Day 21 and Day 35.

All baseline values will be taken from the index procedure (Visit 1).

The last non-missing measurement prior to the index procedure/first treatment will be used as the baseline measurement. This definition of baseline will be used for all effectiveness and safety analyses.

The following conversion factors will be used to convert days into weeks or months or years, or vice versa:

- 1 week = 7 days
- 1 month = 30.4375 days
- 1 year = 365.25 days

8 DEMOGRAPHICS AND OTHER BASELINE CHARACTERISTICS

8.1 DEMOGRAPHICS

Basic summary of demographics by randomization group and overall will be presented. These analyses will be conducted for the ITT Population and the Evaluable Population. The tables will display statistics on age, gender, race, ethnicity, handedness, and education.

8.2 PRIOR AND CONCURRENT MEDICATIONS

A listing will detail all the concurrent medications being taken at baseline along with the randomization group, site, subject ID and whether or not the subject is a member of the Validation Population, for all ITT subjects with a medication recorded in the CRF.

Tables will display the percent and number of subjects who are currently or were previously taking the dementia medication specified in the CRF at baseline by randomization group and overall. One table will be for the ITT Population while another table will be for the Evaluable Population.

8.3 BASELINE AND SCREENING CONDITIONS

Descriptive statistics (N, mean, standard deviation, median, minimum and maximum) will be presented for baseline MMSE total scores and sub-scores by randomization group and overall. One table will be for the ITT Population while another table will be for the Evaluable Population.

The number and percent of ITT subjects who had MRI in past will be presented; the number and percent of these subjects with an MRI in the past will then be presented within each MRI result category. The number and percent of ITT subjects using a cane or other walking aid will be presented. The number and percent of ITT subjects with a lower extremity neurological exam will be presented; the number and percent of these exam subjects (a) with ability to perceive monofilament; and (b) with ability to perceive vibration will be presented by foot (left, right) and overall (both feet combined). These statistics will be presented by randomized group and overall (both randomized groups combined). The analyses will be repeated for the Evaluable Population.

Tables will also be created for the Hamilton-Vaele Contrast Sensitivity score and the Purdue Peg Board Score for both the ITT Population and the Evaluable Population. These tables will display statistics (N, mean, standard deviation, median, minimum, maximum) for the left, right and binocular scores by randomization group and overall.

8.4 BASELINE MEDICAL HISTORY

The number and percent of subjects with a previous medical history and with a current medical history will be presented for each medical history category (e.g., Parkinson's and related conditions, Sleep apnea, Stroke or TIA, etc.). Descriptive statistics (N, mean, standard deviation, median, minimum, maximum) will be presented for total number of traumatic brain injuries. These statistics will be presented by randomized group and overall (only subjects reporting previous traumatic brain injuries will be included). The analyses will be presented for the ITT and Evaluable Populations.

9 EFFECTIVENESS ANALYSES

9.1 PRIMARY EFFECTIVENESS VARIABLE AND ANALYSES (CONSTANT VARIANCE)

Agreement of DCTclock-pen and DCTclock-tablet in assessing cognitive impairment will be assessed by using the Bland-Altman method on the DCTclock total score. The following hypothesis test will be carried out:

$$H_0: Lower_{LoA} \leq -\delta \text{ or } Upper_{LoA} \geq \delta$$

$$H_1: -\delta < Lower_{LoA} < Upper_{LoA} < \delta$$

where $\delta = 30$ is the pre-specified maximum allowable difference, $Lower_{LoA}$ is the lower bound of the two-sided 95% LoA, $Upper_{LoA}$ is the upper bound of the two-sided 95% LoA. The conclusion that the two measurements are in agreement (i.e. equivalent) depends on whether the two-sided 95% CIs of each (lower, upper) LoA are within the boundaries set from the maximum allowable difference.

Specifically, Bland-Altman analysis will consist of the following:

1. Calculate the paired difference in scores between the two tests (i.e., Discrepancy scores) for each subject.
2. Calculate the mean of these paired differences.
3. Calculate the average of the two test results for each subject.
4. Plot the paired differences (y-axis) vs. the average of the two test results (x-axis). This is commonly called the Bland-Altman plot.
5. Calculate a two-sided 95% LoA of the paired differences as: mean difference +/- 1.96*standard deviation (sd) of the differences.

6. Calculate two-sided 95% CI of each (lower, upper) LoA. The formulas for calculating these CIs are as follows:

*Lower: mean difference – 1.96 * sd – (t0.975, N – 1) * sd * sqrt(1/N + 1.96²/(2 * (N – 1))).*

*Upper: mean difference + 1.96 * sd + (t0.975, N – 1) * sd * sqrt(1/N + 1.96²/(2 * (N – 1))).*

where $t0.975, N – 1 * sd$ is the upper 0.025 critical value of the t distribution with $N-1$ degrees of freedom and where N is the sample size.

7. The conclusion that the two measurements are in agreement (i.e. equivalent) depends on whether the CIs constructed from the data are within the boundaries set from the maximum allowable difference. Success is declared on the primary endpoint if the lower CI of the lower LoA is >-30 , and the upper CI of the upper LoA is $<+30$.

The Evaluable Population will be used for these analyses.

A table will summarize the primary effectiveness endpoint. This table will include descriptive statistics for the DCTclock-pen total score, for the DCTclock-tablet total score, for the paired difference between the DCTclock-pen overall score and the DCTclock-tablet overall score (calculated as pen minus tablet), upper and lower LoA and their respective CIs, root mean squared differences (RMSD) as defined in the next section, and ANOVA p-value (for the assessment of homogeneity across randomized groups, as discussed previously). The descriptive statistics will be presented by randomization group and overall.

A figure will display the Bland-Altman plot described above.

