4 SAMPLE SIZE

The primary null and alternative hypotheses are:

$$H_0: LCI_{LLoA} \leq -\delta \text{ or } UCI_{ULoA} \geq \delta$$

$$H_1: -\delta < LCI_{LLoA} < UCI_{ULoA} < \delta$$

where $\delta = 30$ is the pre-specified maximum allowable difference, LCI_{LLoA} is the lower bound of the two-sided 95% confidence interval (CI) for the lower bound of the two-sided 95% limits of agreement (LoA), UCI_{ULoA} is the upper bound of the two-sided 95% CI for the upper bound of the two-sided 95% LoA.

The primary endpoint will be analyzed using Bland-Altman method. This study will produce LoA and associated CIs from the two measurements on each subject (further details are below). The conclusion that the two measurements are in agreement (i.e. equivalent) depends on whether the CIs constructed from the data are within the boundaries set from the maximum allowable difference. An evaluable sample size of 41 subjects achieves at least 90% power to detect agreement when the confidence level of the LoA is 95%, the confidence level of the CIs about the LoA is 95%, and the maximum allowable difference is 30 ($\delta = 30$). The mean and standard deviation of the sample differences are anticipated to be 10 and 7, respectively.

Accordingly, approximately 175 subjects will be enrolled in order to obtain a DCTclock-tablet training dataset of at least 100 subjects and a DCTclock-tablet validation dataset of greater than 41 evaluable subjects.

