9.2 NON-CONSTANT VARIANCE & ASSESSMENT OF SITE HOMOGENEITY

A generative model will be fit of the following form:

$$\begin{aligned} \text{Score Difference} &\sim N(\mu, \sigma) \\ \mu &= \alpha\mu + \beta_1 * \text{Location} + \beta_2 * \text{Test Order} \\ \sigma &= k * \exp(\alpha\sigma + \beta_3 * \text{Average Score}_2 + \beta_4 * \text{Average Score}) \end{aligned}$$

- ‘Location’ and ‘Test Order’ will be one hot encoded indicator variables for the trial location site and order in which the test was given (ie. DCTclock pen assessment first or DCTclock tablet assessment first) respectively.
- Average Score will be calculated as: $(\text{DCTclock pen score} + \text{DCTclock tablet score}) / 2$
- Score Difference will be calculated as: $(\text{DCTclock tablet score} - \text{DCTclock pen score})$
- The parameters k , $\alpha\mu$, and $\alpha\sigma$ are constants

This model will permit the disentangling of site specific impacts and the rate of learning improvement between the first and second assessments while also allowing the variance in score difference to vary as a function of the average score.

The Evaluable Population will be used for this analysis.

Two tables will summarize this model. The first will include the mean estimated coefficient values along with their 96% credible intervals. The second will breakdown the estimated differences in average Score Difference between the site locations and the order in which the assessments were completed. This table will include the mean differences as well as the max 96% prediction interval ranges for each combination of site and order.

A figure will display the 96% prediction intervals for Score Difference (y-axis) as a function Average Score (x-axis) over the range 0 - 100 generated from the fit model above. The Evaluable Population will be plotted over this interval for a visual assessment of the model fit. The max 96% prediction interval range will be added to the figure.

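### The SAP 9.1 confidence limits for the limits of agreement are slightly too narrow on the side that decides success: boundary error 3.6% at N=175 and 4.5% at N=50, against an implied 2.5%

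*SAP*

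**What the plan says.** SAP 9.1 takes the limits of agreement as the mean paired difference ± 1.96 SD. Step 6 reads "Calculate two-sided 95% CI of each (lower, upper) LoA. The formulas for calculating these CIs are as follows", and the half-width that follows is t(0.975, N−1) × SD × √(1/N + 1.96²/(2(N−1))). Only the two outer limits are written out: the lower limit around the lower LoA and the upper limit around the upper LoA. Step 7 uses those two and nothing else: "Success is declared on the primary endpoint if the lower CI of the lower LoA is" above −30 and the upper limit around the upper LoA is below +30. Protocol 10.3.2 asks for the same intervals and rule but gives no formula, so the formula stands in the SAP alone.

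The planning values are in SAP 4: "the maximum allowable difference is 30", "the confidence level of the CIs about the LoA is 95" per cent, and "The mean and standard deviation of the sample differences are anticipated to be 10 and 7, respectively". The primary population is the Evaluable Population (SAP 6.2), and 175 subjects are expected to be available for analysis (SAP 2). SAP 6.3 keeps a fallback: if a tablet-specific model has to be trained, the random subset of 50 takes over, and "this will become the primary population for evaluating effectiveness".

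SAP 9.1 is headed constant variance. SAP 9.2 fits a separate model, "while also allowing the variance in score difference to vary as a function of the average score". That model has no part in the success rule.

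**The concern.** The upper LoA is estimated by mean + 1.96 × SD. When the sample SD comes out low, two things happen together: the estimated LoA is too close to the mean, and the interval around it shrinks, because its width is proportional to the same SD. Both push the outer confidence limit inward. A symmetric t interval does not allow for this, so it under-covers on the outer side and over-covers on the inner side.

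The success rule looks only at the outer side, so the excess error falls in the direction of declaring equivalence. This is the only decision rule for the primary endpoint of a study that the protocol labels pivotal, and the stated confidence level should hold for the limit that decides.

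**Working it through.** **Inputs.** Margin 30, mean 10, SD 7, 95% LoA and 95% CIs (SAP 4). Multiplier 1.96 and the half-width formula (SAP 9.1). N=175 (SAP 2), N=50 (SAP 6.3), N=41 (SAP 4). Neither document prints 2.5%; it follows from a two-sided 95% interval of which one side decides.

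**The plan's own figure.** SAP 4 states "An evaluable sample size of 41 subjects achieves at least 90% power to detect agreement". The usual noncentral-t power approximation reproduces this. At N=41 the standard error is 7 × √(1/41 + 1.96²/80) = 1.884, and the noncentrality for the upper limit is (30 − 10 − 13.72)/1.884 = 3.33. Power is 90.2% (89.4% at N=40). Integrating the actual SAP 9.1 rule over the sampling distributions of mean and SD gives 87.5% at N=41, with 45 needed for 90%. This gap is immaterial at N=175.

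**Outer factor in the SAP.** The upper bound is mean + c × SD, with c = 1.96 + t(0.975, N−1) × √(1/N + 1.96²/(2(N−1))).

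- N=175: 1.96 + 1.9737 × 0.12943 = 2.2155
- N=50: 1.96 + 2.0096 × 0.24331 = 2.4490
- N=41: 1.96 + 2.0211 × 0.26909 = 2.5039

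**Exact error.** For normal differences with one SD σ and mean μ, √N × (μ + 1.96σ − sample mean)/SD follows a noncentral t distribution with N−1 degrees of freedom and noncentrality 1.96√N. With the true upper LoA at +30, the chance that the bound falls below +30 is 1 − F(c√N). The exact factor is the 0.975 quantile of that distribution divided by √N.

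| N | SAP factor | Exact factor | Outer error | Inner error | Total |
|---|---|---|---|---|---|
| 175 | 2.2155 | 2.2389 | 3.55% | 1.54% | 5.09% |
| 50 | 2.4490 | 2.5355 | 4.49% | 0.83% | 5.32% |
| 41 | 2.5039 | 2.6111 | 4.70% | 0.70% | 5.40% |

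A simulation of 2,000,000 trials at N=175 and mean 10 also gave 3.55%, and 2.50% with the exact factor.

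**Dependence on the mean difference (N=175, one LoA at the margin).** Error is 3.55% at mean 10 or 5, 3.1% at mean 2, 1.9% at mean 1 and 0.56% at mean 0. Near zero both limits press on their margins, and both must pass.

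**Effect on the decision at N=175.** At an observed mean of 10 the largest passing SD is 20/2.2155 = 9.03 under the SAP factor and 20/2.2389 = 8.93 under the exact one. At SD 7 the upper bound is 10 + 7 × 2.2155 = 25.51 or 10 + 7 × 2.2389 = 25.67, a shift of 0.16 point. Power at mean 10 and SD 7 is above 99.99% either way.

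**Effect at N=50.** At SD 7 the bound moves by 7 × (2.5355 − 2.4490) = 0.61 point. Power falls from 92.9% to 87.3%; 54 subjects would be needed for 90% with the exact factor.

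**Varying variance (assumed patterns; the documents give none).** N=175, mean 10, population mean + 1.96 SD set to 30, SD log-linear over uniformly spread average scores, 40,000 trials each. By ratio of highest to lowest SD, the SAP rule errs 3.9% (1.5), 4.7% (2), about 6.2% (3), 9.1% (5), 11.5% (8) and 12.8% (10). Scores clustered towards one end give 4.1% to 6.0% for ratios 2 to 4. The exact factor does not cure this: 4.7% at ratio 3 and 10.8% at ratio 10.

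**The case against.** The strongest reply is that step 6 promises a two-sided 95% interval and delivers one: total non-coverage is 5.1% at N=175 and 5.3% at N=50. The formula is the usual approximate Bland-Altman interval and is fully prespecified. Protocol 10.3.1 sets two-sided 5% levels, and the normal-case outer error stays below 5% even at N=50. All of that is true. It does not settle the matter, because only one side of each interval decides, and that is the short side.

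A second reply is that the effect on the decision is tiny. At N=175 the factors differ by about 1%, and at mean 10 the verdict changes only for an observed SD between about 8.93 and 9.03. The 3.6% also needs a true SD of 20/1.96 = 10.2 at mean 10, some 46% above the planned 7. This stands, and it makes the point a modest one at N=175.

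A reader might go further and infer that SAP 9.2 expects the variance to change with score, so that the real error is 6% to 12%. The documents do not support this. SAP 9.2 allows for such variation; it neither predicts it nor gives its size. Errors of that order need roughly a 3-fold to 8-fold change in SD in the log-linear, uniform-score case. Two-group mixtures reach them at smaller ratios (for example about 12.5% with 25% of subjects at SD 12 and 75% at SD 4), but SAP 9.2 describes a smooth function of average score, not two groups. SAP 9.2 also already examines the constant-variance assumption through prediction intervals across the score range.

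**Conclusion.** The point holds in a limited form. The step 6 formula is too narrow on the side that decides success. The one-sided error is 3.6% at N=175 and 4.5% at N=50 instead of the implied 2.5%. These are boundary rates that rest on normal differences, constant variance, a true limit of agreement exactly at the margin, and a mean difference clearly away from zero. They do not say how often the study would err in general: at mean difference 0 and N=175 the rule is conservative, and under the planning values the conclusion is unaffected.

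The point matters mainly if the 50-subject Validation Population becomes primary. Varying variance could raise the error to about 4% to 13% for assumed SD ratios of 1.5 to 10. That is a sensitivity range built on assumptions and not a finding from the documents.

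**What to change.** In SAP 9.1 step 6, compute the outer limits as mean difference ± k × SD, with k the 0.975 quantile of the noncentral t distribution (N−1 degrees of freedom, noncentrality 1.96√N) divided by √N. In R this is `qt(0.975, N-1, ncp = 1.96*sqrt(N))/sqrt(N)`. Leave the ±30 rule in step 7 unchanged and print the current formula as a supportive line.

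The cost at N=175 is one line of wording and code, a bound 0.16 point further out at SD 7, and no material loss of power. At N=50, power at the planning values falls from 92.9% to 87.3%, below the 90% used for planning. State this in SAP 6.3 or SAP 4, and note that 54 subjects would restore 90%.

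For varying variance, add BCa bootstrap outer limits as a sensitivity analysis only, with the number of resamples and the seed fixed in advance. They should not replace the primary limits. They make the result seed-dependent, and at N=175 they still erred 3.5% and 3.9% in two assumed mixture cases (3,000 simulations). At N=50 they erred 4.6% even with normal differences (1,500 simulations).
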